12.1.5.3.3. Monitoring and Management of Elevated LDL-C

Post-randomization, LDL-C results will be masked to investigators in order to maintain the blind. The central laboratory will notify the investigator if the patient's LDL-C level is ≥220 mg/dL. The patient will return to the clinic for a repeat fasting blood lipid sample to confirm that the LDL-C value meets the threshold criteria. The patients will be counseled on healthy dietary guidelines and reminded to take IMP. If confirmed, the patient will discontinue IMP.

12.1.5.3.4. Monitoring and Management of Elevated TG

Post-randomization, TG results will be masked to investigators in order to maintain the blind. The central laboratory will notify the investigator if patient's TG level is >1000 mg/dL. The patients will be counseled on healthy dietary guidelines and reminded to take IMP. The patient will return to the clinic for a repeat fasting blood lipid sample to confirm that the TG value meets the threshold criteria. If confirmed, the patient will discontinue IMP.

12.1.5.3.5. Monitoring and Management of Potential Hypoglycemia and Metabolic Acidosis

Patients will be educated on the signs and symptoms of hypoglycemia. If such signs and symptoms are experienced, patients will be advised to report them to the study site (see Section 13.3 for additional details).

Clinical laboratories will be assessed to determine any signs of anion gap metabolic acidosis. If laboratories are consistent with metabolic acidosis, immediate follow up with the patient for further medical evaluation of the acidosis will occur (see Section 13.3 for additional details). This event should be captured as an AE.

12.1.5.4. Total Blood Volume of Central Clinical Laboratory Samples

The total number of venipunctures and total volume of whole blood collected during the study will be limited to that needed for safety, efficacy, and biomarker assessment. Total whole blood volume collected over the study duration is not to exceed approximately 250 mL for each patient.

13. ADVERSE AND SERIOUS ADVERSE EVENTS

13.1. Adverse Events

13.1.1. Definition of Adverse Events

An AE is defined as any untoward medical occurrence in a clinical investigation patient administered a pharmaceutical product, including control, and which does not necessarily have a causal relationship with treatment. The investigator is responsible for ensuring that any AEs observed by the investigator or reported by the patient are recorded in the patient's medical record.

An AE can be:

- Any unfavorable and unintended sign/symptom including an abnormal laboratory finding or disease temporally associated with the use of a medicinal product, whether or not considered related to the medicinal product
- Any new disease or exacerbation of an existing disease
- Laboratory abnormality or diagnostic test abnormalities (eg, electrocardiogram [ECG] or X-ray) should be reported as an AE if one of the following occurs:
 - Treatment required due to the abnormality
 - Discontinuation of IMP
 - Per Investigator judgement
- TEAEs are defined as AEs that begin or worsen after the first dose of IMP administration as defined in the statistical analysis plan (SAP)

13.1.2. Adverse Drug Reaction

All noxious and unintended responses to a medicinal product related to any dose should be considered an adverse drug reaction (ADR). "Responses" to a medicinal product means that a causal relationship between the medicinal product and an AE is at least a reasonable possibility (ie, the relationship cannot be ruled out).

An unexpected ADR is defined as an adverse reaction, the nature or severity of which is not consistent with the applicable product information (eg, IB for an unapproved investigational product or package insert/summary of product characteristics for an approved product).

13.1.3. Reporting for Adverse Events

All AEs occurring during the course of the study (starting from signing informed consent through 30 days after study completion/discontinuation) will be collected on the AE eCRF. Patients should be instructed to report any AE that they experience to the investigator. Investigators should make an assessment for AEs at each visit and record the event on the appropriate AE eCRF.

Wherever possible, a specific disease or syndrome rather than individual associated signs and symptoms should be identified by the investigator and recorded on the eCRF. However, if an observed or reported sign or symptom is not considered a component of a specific disease or syndrome by the investigator, it should be recorded as a separate AE on the eCRF. Additionally, the condition that led to a medical or surgical procedure should be recorded as an AE, not the procedure.

Any medical condition already present at screening or baseline should not be reported as an AE unless the medical condition or signs or symptoms present at baseline worsens in severity or seriousness at any time during the study. In this case, it should be reported as an AE.

It is the responsibility of the investigator to assess the clinical significance of all abnormal values as defined by the list of reference ranges from the local laboratory. In some cases, significant changes in lab values within the normal range will require similar judgment.

An abnormal laboratory value that is not already associated with an AE is to be recorded as an AE only if any one of the following criteria is met:

- an action on the study drug is made as a result of the abnormality
- intervention for management of the abnormality is required
- at the discretion of the investigator should the abnormality be deemed clinically significant

Significant abnormal laboratory values occurring during the clinical study will be followed until repeat tests return to normal, stabilize, or are no longer clinically significant. Any abnormal test that is determined to be an error does not require reporting as an AE.

Each AE is to be evaluated for duration, severity, seriousness, and causal relationship to the IMP. For each AE, the following information will be recorded:

- Description of the event (eg. headache)
- Date of onset
- Date of resolution (or that the event is continuing)
- Action taken as a result of the event
- Seriousness of the event
- Severity of the event
- Outcome of the event
- Investigator's assessment of relationship to IMP.

A cluster of signs and symptoms that results from a single cause should be reported as a single AE (eg, fever, elevated white blood cells [WBC], cough, abnormal chest X-ray, etc, can all be reported as "pneumonia").

The investigator will carefully evaluate the comments of the patient and the response to treatment in order that he/she may judge the true nature and severity of the AE. The question of

the relationship of AEs to IMP administration should be determined by the investigator or study physician after thorough consideration of all facts that are available.

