6. INVESTIGATIONAL PLAN

6.1. Overall Study Design

This is a Phase 2, multicenter, randomized, double-blind, placebo-controlled, parallel group study. Patients will initially undergo screening at Week -6 (Visit S1). Eligible patients will begin washout of all LDL-C-lowering drugs and nutritional supplements at least 5 weeks prior to randomization. Patients will return at Week -1 (S2) for lipid and/or other assessments. Patients who are deemed not eligible for randomization at any point during screening will be notified by clinical site personnel and considered screen failures. At Week 0 (Visit T1), approximately 60 patients will be randomized in a ratio of 2:1 to receive either triplet therapy (bempedoic acid 180 mg + ezetimibe 10 mg + atorvastatin 20 mg) or placebo once daily for 6 weeks. Randomized patients will return for clinic visits at Week 3 (Visit T2) and Week 6 (Visit T3).

For details of study assessments, see the Schedule of Events in Appendix 1.

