7. SELECTION OF PATIENTS

7.1. Subject Inclusion Criteria

Each patient must meet the following criteria to be eligible for this study.

- 1. Provision of written informed consent prior to any study-specific procedure;
- 2. Age ≥18 years or legal age of majority based on regional law, whichever is greater, at Week -6 (Visit S1);
- 3. Fasting calculated LDL-C between 130-189 mg/dL at Week -1 (Visit S2) following washout of all LDL-C-lowering drugs and nutritional supplements;
 - Note: LDL-C may be repeated 1 time with the screening period extended up to 1 week. For those patients who have a repeat LDL-C, the mean of the first value and the repeat value will be used to determine eligibility.
- 4. Patient is sufficiently stable and suitable to undergo washout of all LDL-C-lowering drugs and nutritional supplements for 12 weeks (with potential for 1 week extension) based on Investigator assessment;
- 5. Men and nonpregnant, nonlactating women. Women must be one of the following:
 - a. Naturally postmenopausal defined as ≥ 1 year without menses and:
 - i. \geq 55 years, or
 - ii. <55 years with follicle-stimulating hormone (FSH) ≥40.0 IU/L, or
 - b. Surgically sterile including hysterectomy, bilateral oophorectomy, and/or tubal ligation, or
 - c. Women of childbearing potential willing to use one acceptable method of birth control during the study and for 30 days after the end of treatment including:
 - i. birth control medications,
 - ii. placement of an intrauterine device with or without hormones,
 - iii. barrier methods including condom or occlusive cap with spermicidal foam or spermicidal jelly,
 - iv. vasectomized male partner who is the sole partner for this patient,
 - v. true abstinence (not including periodic abstinence such as calendar, ovulation, symptothermal, postovulation methods, or withdrawal);

There are no protocol-specific birth control requirements for men with partners who are able to become pregnant.

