10.5. Procedures and Schedule of Assessments

The study is comprised of 2 distinct periods: screening and double-blind treatment.

The schedule of study events is provided in Appendix 1. However, a patient can be seen at any time for reasons of safety.

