10.5.4. Treatment Week 3 (Visit T2; Day 22 ± 3 days)

Patients will undergo the following assessments and procedures at Week 3 (Visit T2):

- Concomitant medication review (ongoing)
- Assess AEs and SAEs
- Weight
- Vital signs
- Central clinical laboratory evaluations:
 - Hematology, blood chemistry, and urinalysis
 - Basic fasting lipids (TC, calculated LDL C, HDL C, non-HDL C, and TG)
- Return of IMP; assessment and recording of IMP dosing adherence
- IWRS contact to obtain new MED ID number for double-blind IMP
- Dispense double-blind IMP and provide dosing and storage instruction
- Dietary and lifestyle counselling

10.5.5. Treatment Week 6 (Visit T3; Day 43 ± 3 days)/End of Study or Early Termination

Patients will undergo the following assessments and procedures at Week 6 and/or End of Study/Early Termination:

- Concomitant medication review (ongoing)
- Assess AEs and SAEs
- PE
- Weight
- Vital signs
- Central clinical laboratory evaluations:
 - Hematology, blood chemistry, and urinalysis
 - Basic fasting lipids (TC, calculated LDL-C, HDL-C, non-HDL-C, and TG)
 - ApoB and hs-CRP
- Return of IMP; assessment and recording of IMP adherence

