10.6. Patient Withdrawal From the Study

Patients must remain in the study until the last scheduled visit at Study Day 43 (Visit T3) to be considered as having completed participation in the study.

The patient's decision to participate in the clinical study is voluntary. Patients may refuse to continue in the study and/or withdraw from participation in this study at any time, for any reason,

specified or unspecified, and without penalty or loss of benefits to which the patient is otherwise entitled.

It is the right and duty of the Investigator to interrupt the treatment of any patient whose health or well-being may be threatened by continuation in this study. Such patients should be withdrawn from the study and should not be continued under a modified regimen.

Patients who are withdrawn from the study may not re-enter. The reasons for withdrawal from this study may include:

- AE
- Patient's withdrawal of consent
- Failure to comply with the protocol
- Lost to follow-up
- Illness, condition, or procedural complication affecting the patient's ability to participate or requiring prohibited medication
- The Sponsor or Investigator terminates the study
- In the Investigator's judgment, it is deemed in the best interest of the patient to discontinue his/her participation in the study
- Any other reason

If a patient is lost to follow-up, every reasonable effort must be made by the clinical site personnel to contact the patient and determine the reason for discontinuation/withdrawal. The measures taken to follow-up must be documented.

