# 5.4 Safety Endpoints and Analyses

For all safety endpoints, the safety population (SP) will be used. Descriptive summary will be provided for safety endpoints.

The summarization of AEs will include only TEAEs (defined as AEs that begin or worsen after the first dose of double-blind IMP until 30 days after last dose of IMP). All TEAEs, SAEs, AEs leading to withdrawal of IMP, fatal AEs and AEs of special interest will be summarized by MedDRA SOC and preferred term in descending order of frequency by treatment group.

Clinical safety laboratories, including hematology, blood chemistry, glucose, and urinalysis; PE findings; vital signs; and weight will be summarized by the value and by change or percent change from baseline in the value (where appropriate) at each postbaseline time point.

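### New adverse events count for 30 days after treatment, but no patient contact is scheduled after Week 6, so about 40% of the nominal TEAE window has no scheduled enquiry

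*Protocol*

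**What the plan says.** **Windows.** Protocol 13.1.3 collects all AEs, not only serious ones, "starting from signing informed consent through 30 days after study completion/discontinuation". Protocol 13.2.2 applies the same end point to SAEs, and 13.2.3 to deaths. SAP 5.4 limits the AE summaries to TEAEs, which "begin or worsen after the first dose of double-blind IMP until 30 days after last dose of IMP". SAP 5.2.7 counts as concomitant any drug started within 30 days of the last dose. Protocol 7.1, criterion 5c, requires women of childbearing potential to be "willing to use one acceptable method of birth control during the study and for 30 days after the end of treatment".

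**Contacts.** Protocol 10.5 states: "The study is comprised of 2 distinct periods: screening and double-blind treatment". Protocol 10.6 defines completion: "Patients must remain in the study until the last scheduled visit at Study Day 43". The heading of Protocol 10.5.5 makes that visit the last for everyone: "Treatment Week 6 (Visit T3; Day 43 ± 3 days)/End of Study or Early Termination". Protocol Appendix 1 and SAP Appendix 1 both end at that column. Investigators are to assess AEs at every visit (Protocol 13.1.3) and ask about medication at every clinic visit (Protocol 8.2). Protocol 13.2.2 mentions a 30-day follow-up period, but neither schedule contains one.

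**The concern.** Incidence of AEs is a listed safety endpoint (Protocol 5.2.3; SAP 3.2.3). Up to Week 6 its numerator comes from direct questioning at visits. For the next 30 days new events enter only if a patient volunteers them or the site learns of them by chance. The two kinds of ascertainment are then added into one TEAE percentage, and into incidence rates and risk differences where SAP 5.4.1 uses them. A reader of the table would take the whole window as equally observed.

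Two other items depend on the same missing contact.

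- **Restarted lipid drugs.** The washout in inclusion criterion 4 lasts 12 weeks, which is 6 of screening plus 6 of treatment, so it ends at the Week 6 visit. Nothing in the protocol prevents a patient from restarting a lipid drug afterwards. A muscle event on a restarted statin would be a TEAE in either arm, and muscle events are of special interest (Protocol 13.3; SAP 5.4.2). SAP 5.2.7 would count the restarted drug as concomitant, but nobody is scheduled to ask about it.
- **Pregnancy.** Tests are scheduled only at S1 and T1. Protocol 13.2.4 requires a report once a pregnancy is known, but no one is due to ask during the 30-day contraception period.

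**Working it through.** The documents give no figure for this point, so there is none to reproduce. The check compares the length of the TEAE window with the part that falls after the last scheduled enquiry.

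**Inputs**
- Treatment: triplet therapy "or placebo once daily for 6 weeks" (Protocol 6.1), i.e. 42 days.
- TEAE window: Day 1 to last dose + 30 days (SAP 5.4).
- Last enquiry: the Week 6 visit, Day 43 ± 3 (Protocol 10.5.5).
- On clinic days IMP is held until procedures are finished (Protocol 8.1), and IMP is returned at Week 6. The last dose is therefore nominally on Day 42, the day before the visit.

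**Nominal share.** Days after the last dose / TEAE window = 30 / (42 + 30) = 30/72 = 41.7%.

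**Sensitivity to day counting.** Uncovered days = (last dose + 30) − visit day. Share = uncovered days / (last dose + 30).

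| Visit day | Last dose | Window (days) | Days after visit | Share |
|---|---|---|---|---|
| 40 | 39 | 69 | 29 | 42.0% |
| 40 | 40 | 70 | 30 | 42.9% |
| 43 | 42 | 72 | 29 | 40.3% |
| 43 | 43 | 73 | 30 | 41.1% |
| 46 | 45 | 75 | 29 | 38.7% |
| 46 | 46 | 76 | 30 | 39.5% |

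The range for completers is 38.7% to 42.9%. A patient who leaves early has a shorter treated period and hence a larger share. A patient who stops IMP but stays to Week 6 has a smaller share.

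**The anchors differ.** The protocol window runs from study completion or discontinuation, the SAP window from the last dose. For completers they differ by about a day. Take instead a patient who stops IMP on Day 10 and attends Week 6 on Day 43:
- SAP window ends on Day 10 + 30 = Day 40, before the last visit.
- Protocol window ends on Day 43 + 30 = Day 73.

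A call timed only from the last dose would fall on Day 40, before the Week 6 visit, and would leave the rest of the protocol window without a prompt. SAP 5.4.1 adds a further anchor, the last study visit, for following ongoing AEs.

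**Weight of one patient.** About 60 patients randomized 2:1 gives roughly 40 and 20. One patient whose only event goes unrecorded changes an arm's incidence by 1/40 = 2.5 or 1/20 = 5 percentage points.

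**The case against.** The plan does not go silent after Week 6. Sites are to tell patients to report any event (Protocol 13.1.3), and a patient can be seen at any time for safety (Protocol 10.5). AEs that are serious or led to discontinuation are followed until resolved or stable (Protocol 12.1). AEs requiring discontinuation from the study get repeat assessments, and ongoing IMP-related AEs are followed for up to 30 days (Protocol 13.1.6). SAP 5.4.1 extends that follow-up to all ongoing AEs. SAEs are reported for 30 days (Protocol 13.2.2). A volunteered muscle event would normally bring a restarted statin to light, because causality is to be judged on all available facts (Protocol 13.1.3). Safety analysis is descriptive, and the study is a small 6-week Phase 2 trial.

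Most of this stands, and it narrows the point. A reader might infer that nothing at all captures events after Week 6; the routes just listed contradict that. A reader might also infer that early-termination patients are left without follow-up, but those who stop because of an AE have explicit continuing follow-up. Nor can it be said that patients receive no reporting card, because consent pages are not part of the reviewed text.

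The objection does not supply a scheduled prompt for new events. Following a known AE does not detect another one, and the additional contacts in Protocol 10.2 concern the IWRS, not patients. SAP 5.2.7 defines the restarted drug as concomitant without providing a contact at which to record it.

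**Conclusion.** The mismatch is real, and correcting it is a worthwhile, inexpensive improvement. About 40% of the nominal TEAE window (30/72 = 42%; about 39–43% for completers) has no scheduled enquiry for new AEs. New, mainly non-serious, post-treatment events, restarted lipid drugs and pregnancies may be under-recorded. The figure assumes dosing to about Week 6 and a final visit within its window.

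Two stronger readings are not supported. The first is that 42% of TEAEs, or some calculable fraction of them, would be lost. With onset even over the window and 25–50% of later events volunteered, the missed share would be 0.417 × 0.50 = 21% to 0.417 × 0.75 = 31%. The documents support neither assumption, and off-drug days probably carry fewer events, so this range is not a finding. The second is that the gap biases the comparison of arms. The schedule is the same in both arms, and no difference in reporting is shown. The demonstrated weakness is incomplete and mixed ascertainment in a stated safety endpoint. Efficacy analyses are unaffected.

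**What to change.** 1. **Schedule a contact.** Add to Protocol 10.5 and to both schedules of events one telephone contact about 30 days after study completion or discontinuation, and no earlier than 30 days after the last dose. Apply it to completers and early discontinuers alike. Record new AEs and SAEs, status of open AEs, drugs started with dates, and pregnancy.
2. **Use one anchor.** State a single, consistent reference point for the 30-day window in Protocol 13.1.3, 13.1.6 and 13.2.2 and SAP 5.4 and 5.4.1.
3. **Split the table.** In SAP 5.4.1, tabulate TEAEs with onset on treatment separately from those with onset after the last dose.

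**Cost.** About 60 short calls by existing site staff, one eCRF page and one further table split. Last patient contact moves about 30 days later, within a period when AE collection is already required.

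Ending both windows at the last visit would also remove the mismatch, but it would give up post-treatment information that the protocol now commits to collecting.

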13.1.4. Severity

It is the investigator's responsibility to assess the intensity (severity) of an AE.

The severity of the AE will be characterized as mild, moderate, or severe according to the following definitions:

- Mild: Events are usually transient and do not interfere with the patient's daily activities
- Moderate: Events introduce a low level of inconvenience or concern to the patient and may interfere with daily activities
- Severe: Events interrupt the patient's usual daily activity, are incapacitating with inability to do usual activities, or significantly affect clinical status and warrant intervention and/or close follow-up

Note: A severe AE need not be serious and an SAE need not, by definition, be severe.

13.1.5. Relationship

It is the investigator's responsibility to assess the relationship between the IMP and the AE. The degree of "relatedness" of the AE to the IMP may be described using the following scale:

- Not Related: No temporal association and other etiologies are likely the cause
- Unlikely: While cannot be definitively ruled as not related to IMP, a causal association is remote, and other etiologies are more likely to be the cause. For reporting and summarization, events assessed as Unlikely to be related to IMP will be considered as Not Related to IMP.
- Possible: Temporal association, but other etiologies are likely the cause. However, involvement of the IMP cannot be excluded.
- Probable: Temporal association, other etiologies are possible but unlikely. The event may respond if the IMP is discontinued.
- Definite: Established temporal association with administration of the IMP with no other more probable cause. Typically, the event should resolve when the IMP is discontinued and recur on re-challenge.

